8.5 Post-Treatment Efficacy Observations

While short-term double-blind treatment period (up to and including the start of long-term treatment period, where applicable) efficacy observations will be listed regardless of whether the subject was taking study drug, observations may not contribute to summaries/analyses if they are measured after the last dose of short-term double-blind study medication (up to and including the start of long-term treatment period, where applicable) as indicated below:

- Lipids, glucagon, proinsulin, uACR, biomarkers (C-reactive protein, N-terminal ProB-type Natriuretic Peptide) and SBP will be summarized only if measured on or prior to the 4th day after the last study drug treatment date.
- FPG, fasting C-peptide, fasting insulin, HOMA assessments and spot urinary glucose to creatinine ratio will be summarized/analyzed only if measured on or prior to the first day after the last study drug treatment date.
- HbA1c, body weight, BMI, and waist circumference will be summarized/analyzed only if measured on or prior to the 8th day after the last study drug treatment date.

Similar rule applies for the combined short- and long-term treatment periods.

8.6 Assignment of Doses to Adverse Events and Laboratory Assessments

In case of missing dates, prior to assigning the treatment that the subject received at the onset of an AE or at the time of a laboratory assessment, imputation rules will be applied as follows:

For AEs, a missing or incomplete onset date will be imputed according to the following conventions:

- If the onset date for an AE is missing or incomplete, an imputed date will be derived to slot the event to an appropriate analysis period. This derived date will not be reported in summary tables or listings. Every effort will be made to determine the actual onset date for the event or to obtain a reliable estimate for the onset date from the investigator.
- If an onset date is missing, the derived onset date will be calculated as the first non-missing valid date from the following list (in order of precedence):
 - First active study medication date
 - Consent date
 - Visit date corresponding to the visit at which the event was reported.
 - If a valid non-missing date is not available for any of these dates, the derived onset date will be set to missing.
- If an onset date is incomplete, the derived onset date will be calculated using the following algorithm:
 - Calculate a surrogate date as the first non-missing valid date from the following list (in order of precedence):
 - ◆ First active study medication date
 - ◆ Consent date
 - ◆ Visit date corresponding to the visit at which the event was reported
 - ◆ If a valid non-missing date is not available for any of these dates, the surrogate date will be set to missing.
 - Based on the information provided, set the derived date to the earliest possible date. If only a year is provided, set the derived date to January first of that year. If a year and month is provided, set the derived date to the first day of that month.
 - If the surrogate date is non-missing then:
 - ◆ If the derived date is on or after the surrogate date use the derived date as calculated
 - ◆ If the derived date is prior to the surrogate date and the surrogate date is consistent with the partial data provided for the onset date, use the surrogate date as the derived date
 - ◆ If the derived date is prior to the surrogate date and the surrogate date is not consistent with the partial data provided for the onset date then set the derived onset date to be the latest possible date based on the partial onset date information provided. If only a year is provided, set the derived date to December 31st of that year. If a year and month is provided, set the derived date to the last day of that month.
 - If all three dates used to determine the surrogate date are missing, then based on the information provided, set the derived date to the earliest possible date. If only a year is provided, set the derived date to January first of that year. If a year and month is provided, set the derived date to the first day of that month.

A drug treatment file will be created, containing any starting and stopping dose as well as intermediate dose changes within each study period, with dates as recorded on the CRF. In this context,

- The date of the first dose of study medication is defined as the earliest start date with number of tablets > 0 reported on the study medication page.
- Date of the last dose of study medication is defined as the latest start or stop date with number of tablets > 0 reported on the study medication page.

8.7 Concomitant Medications

Start and stop date of all concomitant medications are collected on the CRF. In order to classify medication as prior, current or concomitant, partial, missing or invalid start and stop dates will be imputed where possible as follows:

- If the reported start date is missing or invalid and the informed consent date is not missing or invalid, then the imputed start date is set equal to the informed consent date. If the consent date is missing or invalid and the birth date is not missing or invalid, then the imputed start date is set equal to the birth date. If the start date, the consent date and the birth date are all invalid or missing, then the imputed start date is set equal to missing.
- If the reported start date is partially entered, then the imputed start date is set equal to the earliest possible reported start date based on the partial entered reported start date.
- If the reported end date is missing, continuing, unknown or invalid, then the imputed end date is set equal to the most recent database extraction date.
- If the reported end date of the medication is partial, then the imputed end date is set equal to the last possible reported end date based on the partial entered reported end date.

Imputed dates will not appear on the listings of non-study medication.

8.8 Counting Rules for Adverse Events

Where a subject has the same adverse event, based on preferred terminology, reported multiple times in a single analysis period, the subject will only be counted once at the preferred terminology level in adverse event frequency tables.

Where a subject has multiple adverse events within the same system organ class in a single analysis period, the subject will only be counted once at the system organ class level in adverse event frequency tables.

When a subject has the same adverse event, based on preferred terminology, reported multiple times in a single analysis period, the following criteria, in order of precedence, will be used to select the event to be included in summary tables:

- Relationship to study medication
- Intensity of event
- Onset date
- Related events will take precedence over unrelated events in determining the event to include in summary tables.

- More intense events will take precedence over less intense events in determining the event to include in summary tables.
- Earlier onset date events will take precedence over late onset date events in determining the onset to include in summary tables.

When reporting adverse events by intensity, in addition to providing a summary table based on the event selection criteria detailed above, summary tables will also be provided based on the most intense event during the analysis period - independent of relationship to study medication. For these tables, the following criteria, in order of precedence, will be used to select the event to be included in summary tables:

- Intensity of event
- Onset date

8.9 Fasting State

Lipids parameters listed in the protocol include Total -C, LDL-C, HDL-C, and TG. For lipid parameters, only data collected in fasting state will be used for analysis. For FPG, fasting insulin, and fasting C-peptide, only assessments documented with the subject in fasting state will be summarized and listed.

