Glimepiride 1-6 mg or matching placebo capsules, administered orally once daily, will be provided for the 156-week blinded treatment period. During the first 12 weeks, the glimepiride dose will be slowly titrated in a stepwise blinded fashion depending on glycemic control. For the duration of the study, FPG will be measured at the study center using a glucose analyzer provided by the Sponsor. The investigator's decision on dose titration (either upwards if no issues with hypoglycemia or downwards if recurrent hypoglycemia occurs) will take both the plasma glucose measurements (measured prior to the visit), and the investigator's measurements at the titration visits, into account. The glimepiride dose will be titrated to optimal effect (FPG ≤ 110 mg/dL [≤ 6.1 mmol/L]) or the highest tolerable dose during the first 12 weeks. The starting dose for glimepiride is 1 mg per day (once daily), which can be further increased by increments of 1-2 mg at 3-week intervals to a maximum of 6 mg per day (maximum recommended dose in the Summary of Product Characteristics⁹ and thus the maximum dose to be used in this study). The titration steps will be 2 mg, 3, mg, 4 mg, and 6 mg once daily if needed. In subjects for whom titration is not medically indicated at Week 3, re-assessment for titration will occur at Week 6, Week 9, and Week 12.

The glimepiride dose can be down-titrated during the titration period if hypoglycemic events occur. The treatment can thereafter be up-titrated once during the titration period. Subjects whose IMP dose was up-titrated to the maximum level will have a follow-up phone call 3 weeks later. The glimepiride dose can be down-titrated from Week 12 onwards (maintenance period) if hypoglycemic events occur.

During the randomized treatment period, diet and life-style modification will continue to be reinforced.

All randomized subjects who are rescued and taking randomized IMP should continue to attend scheduled study visits as planned in the time and events table ([Section 5](#)).

Subjects who decide to prematurely discontinue the IMP will always be asked about the reason(s) for discontinuation and the presence of any AEs. Subjects should return and complete the procedures described for the End of Treatment (EOT) visit as soon as possible, but at the latest 7 days after discontinuation of IMP. Subjects with unresolved AEs should also be followed-up as long as medically indicated as judged by the investigator.

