Review concomitant medications / procedures	X	X	X	X	X	X	X	X		X	
Provide diet and exercise counseling	X	X	X	X	X	X	X	X		X	Section 5.8.1 (in protocol)
Provide glucose meter supplies / instructions	X	X	X	X	X	X	X	X		X	
Provide logs/ instructions	X	X	X	X	X	X	X	X		X	
Review study logs	X	X	X	X	X	X	X	X		X	
Assess AEs and hypoglycemia episodes	X	X	X	X	X	X	X	X		X	Section 5.3.1.2 (in protocol)

Table 5.1-2: Short-term Procedural Outline CV181-365 (52-week) Double-blinded Treatment (Period C, Day 1 to Week 52)

Procedure	Rand Day 1 ^{a,b}	Wk 3 ^b	Wk 6 ^b	Wk 9 ^b	Wk 12 ^b	Wk 16 ^b	Wk 28 ^b	Wk 40 ^b	Wk 51 ^c	Wk 52 Rescue / D/C ^b	Notes
Central Laboratory											
Pregnancy test (urine) WOCBP only	X	X	X	X	X	X	X	X		X	Home pregnancy test kits sent home with WOCBP subjects to perform pregnancy test between visits and record result in log book
Clinical chemistry, haematology, urinalysis (standard safety laboratory panel)	X	X	X		X		X			X	
Microscopic urinalysis					X					X	Section 5.3.2 (in protocol) Appendix 3 (in protocol)
Spot urine for glucose, albumin and creatinine quantification and determination of glucose:creatinine and albumin:creatinine ratios	X						X			X	
HbA1c	X				X	X	X	X		X	
FPG	X	X	X	X	X	X	X	X		X	
Estimated CrCl (Cockcroft-Gault) and serum creatinine (SCr)	X	X	X	X	X	X	X	X		X	
Fasting Serum Lipids (Total-C, LDL-C, HDL-C, TG)	X									X	
Fasting serum insulin and proinsulin for proinsulin/insulin ratio, C-peptide, and glucagon	X									X	
hsCRP, NT-proBNP	X									X	

Table 5.1-2: Short-term Procedural Outline CV181-365 (52-week) Double-blinded Treatment (Period C, Day 1 to Week 52)

Procedure	Rand Day 1 ^{a,b}	Wk 3 ^b	Wk 6 ^b	Wk 9 ^b	Wk 12 ^b	Wk 16 ^b	Wk 28 ^b	Wk 40 ^b	Wk 51 ^c	Wk 52 Rescue / D/C ^b	Notes
Additional Assessments											
Patient reported outcomes questionnaires	X						X			X	Section 5.8.8 (in protocol)

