8.3.1 Post-treatment Efficacy and Safety Evaluations

While efficacy and safety observations will be listed regardless of whether the subject was taking double-blind study drug, observations may not contribute to summaries/analyses if they are measured after the last dose of the double-blind study medication given during the treatment periods, as indicated below:

For efficacy parameters:

- Lipids, glucagon, proinsulin, uACR, biomarkers (C-reactive protein, N-terminal ProB-type Natriuretic Peptide) and SBP will be summarized only if measured on or prior to the 4th day after the last study drug treatment date.
- FPG, fasting C-peptide, fasting insulin, HOMA assessments and spot urinary glucose to creatinine ratio will be summarized/analyzed only if measured on or prior to the first day after the last study drug treatment date.
- HbA1c, BMI, waist circumference and body weight will be summarized/analyzed only if measured on or prior to the 8th day after the last study drug treatment date.

For safety parameters:

- SAEs, including hypoglycemia, reported as SAEs, and the lab measurements for the liver function tests will be included in the summaries only if occurred/measured on or prior to the 30th day after the last study drug treatment date.
- All other safety events (non-serious AEs, non-serious hypoglycemia, etc.) and measurements (safety lab, vital signs, etc.) will be included in the summaries only if occurred/measured on or prior to the 4th day after the last study drug treatment date.

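### SAP 8.9 leaves glucagon and proinsulin out of the fasting-sample restriction, although the protocol schedules them as fasting in the same row as insulin

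*SAP*

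**What the plan says.** Protocol Table 5.1-2 schedules one row at Day 1 and at the combined Week 52/rescue/discontinuation visit: "Fasting serum insulin and proinsulin for proinsulin/insulin ratio, C-peptide, and glucagon". In Table 5.1-3, at Week 156/rescue/discontinuation, insulin, proinsulin and glucagon again share one fasting row. C-peptide has its own fasting row there, drawn at Week 91 as well.

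SAP 8.9 restricts two groups of analytes. For lipids: "For lipid parameters, only data collected in fasting state will be used for analysis". For glucose and hormones: "For FPG, fasting insulin, and fasting C-peptide, only assessments documented with the subject in fasting state will be summarized and listed". Glucagon and proinsulin appear in neither group.

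SAP 7.5.5.2 analyses change from baseline in glucagon, C-peptide, proinsulin, insulin and iHOMA2 with the ANCOVA model of SAP 7.1.3, which uses the baseline value as covariate. SAP 7.5.5 makes no multiplicity adjustment for exploratory endpoints and presents nominal p-values only.

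Separately, SAP 8.3.1 limits which values count once dosing has stopped. Glucagon and proinsulin have a limit of 4 days: "glucagon, proinsulin, uACR, biomarkers (C-reactive protein, N-terminal ProB-type Natriuretic Peptide) and SBP will be summarized only if measured on or prior to the 4th day". Insulin and C-peptide have a limit of 1 day: "fasting C-peptide, fasting insulin, HOMA assessments and spot urinary glucose to creatinine ratio will be summarized/analyzed only if measured on or prior to the first".

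**The concern.** The protocol treats fasting as a condition of the draw for all of these hormones, but the SAP enforces it for only some of them. If a subject arrives unfasted, or fasting is not recorded, the same visit's blood is rejected for insulin and C-peptide and accepted for glucagon and proinsulin. Members of one metabolic family, analysed with one model, would then rest on different rules for what counts as a valid sample.

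Two features make a single unfasted sample harder to absorb. In the short-term period this row is drawn only at Day 1 and at Week 52, rescue or discontinuation, so there are no intermediate values of glucagon or proinsulin. In addition, the Day 1 value enters the model twice: it is subtracted to form the change, and it is also the covariate.

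**Working it through.** The plan states no figure on this point, so the check sets the rules side by side.

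**Inputs**
- Fasting restriction (SAP 8.9): insulin and C-peptide yes; lipids yes; glucagon and proinsulin no.
- Limit after last dose (SAP 8.3.1, repeated in 8.5 and Section 12): insulin and C-peptide 1 day; glucagon, proinsulin and lipids 4 days. SAP 7.6.6 also gives glucagon and proinsulin 4 days.

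**Rule.** A value is kept if days since last dose ≤ limit, and either the sample is documented as fasting or no fasting restriction applies.

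| Sample | Days since last dose | Insulin, C-peptide | Glucagon, proinsulin | Lipids |
|---|---|---|---|---|
| Fasting | 0–1 | kept | kept | kept |
| Fasting | 2–4 | dropped | kept | kept |
| Not documented as fasting | 0–4 | dropped | kept | dropped |
| Either | 5 or more | dropped | dropped | dropped |

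The third row is the fasting gap. It arises at any visit, including Day 1 and on-treatment visits, and does not depend on discontinuation. The lipid column shows that membership of the 4-day group does not explain it: lipids share that limit and are still restricted to fasting samples.

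**Effect on the treatment difference.** Assume that an unfasted value differs from a fasting one by an average shift d; the protocol's fasting label implies that this matters, but the documents give no value. Let p be the share of unfasted samples at a visit in one arm.
- That arm's mean moves by p × d.
- The difference between arms moves by p₁d₁ − p₀d₀, which is zero if the share and the shift are equal in the two arms.
- The variance within each arm rises by p(1 − p)d², taking d as constant and the underlying fasting variance as unchanged.

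Day 1 samples precede treatment, so randomization balances unfasted baselines in expectation. After baseline the trial is double-blind, and nothing in the documents points to different unfasted rates by arm. The expected consequence is therefore extra noise rather than a directional bias. Neither p nor d is given, so no numerical size can be stated.

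**The case against.** The strongest reply is that exposure is narrow. The draws are scheduled as fasting, so an unfasted value enters only through non-adherence or missing documentation. The endpoints are exploratory; Protocol 8.4.2.3 says such endpoints will not be statistically tested, and the SAP gives nominal p-values only. All of this stands and limits the weight of the point. It does not explain why two of the hormones in one fasting row are left out.

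Four stronger readings are tempting, and the documents support none of them.

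- **The 1-day and 4-day limits are a mistake.** A reader might infer this because the end-of-treatment visit is due "as soon as possible, but at the latest 7 days after discontinuation of IMP", so a draw on days 2 to 4 can count for two hormones and not for the other two. But the split is stated identically in SAP 8.3.1, 8.5 and Section 12, and the SAP uses analyte-specific limits throughout (1, 4, 8 and 30 days). The 1-day group holds glucose, insulin, C-peptide and the HOMA indices, which is a coherent grouping. It may be deliberate, although no reason is given. Some SAP 8.4 windows also end on the last treatment day, which could narrow the effect further; none of them names glucagon or proinsulin.
- **The proinsulin/insulin ratio is lost.** The ratio appears in the schedule row's label but is not an endpoint in either document.
- **A material bias follows.** No unfasted rate and no fed-to-fasting shift is given, and similar rates in the two arms would largely cancel in the difference.
- **Days 2 to 4 represent a share of samples.** The 7 days are an outer limit, the visit is due sooner if possible, and only subjects who stop treatment early are exposed.

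**Conclusion.** The gap in SAP 8.9 is real. Samples not documented as fasting are excluded for insulin and C-peptide and retained for glucagon and proinsulin, contrary to the protocol's own fasting label, and the SAP gives no reason. The gap changes which values enter two planned ANCOVA endpoints, at baseline and at follow-up.

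Severity is minor. The likely effect is noise in exploratory results, on the assumption that unfasted samples are about equally frequent and similarly shifted in the two arms. Their number cannot be derived from the documents. The primary analysis, the secondary endpoints and the testing hierarchy do not use these analytes.

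The differing post-dose limits are not shown to be an error and form no part of this conclusion.

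**What to change.** In SAP 8.9, add glucagon and proinsulin to the list restricted to samples documented as fasting. If keeping unfasted values of these two was intended, state that and give the reason. Optionally, add one sentence in SAP 8.3.1 explaining why the post-dose limit is 1 day for insulin, C-peptide and HOMA and 4 days for glucagon and proinsulin; no change to either limit is needed.

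The cost is one line of SAP wording and the loss of a few unfasted values. Table 5.1-1 schedules no earlier glucagon or proinsulin draw, so a subject whose Day 1 sample was unfasted would have no baseline for these two analytes and would leave their ANCOVAs, as already happens for insulin. The SAP's amendment history shows that the short-term report preceded Version 3, so any rerun of the Week 52 results should be labelled as a change made after reporting.

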8.10 Percent Compliance Calculation

See Section 7.4.3.

8.11 Strip Sign for Selected Laboratory Data

For selected laboratory test values that have been received with an operator sign as a part of the result (>, ε, <, or δ), a process to strip the operator sign will be applied and the resulting numeric values will be used for data analysis. The raw value with operator will remain as such on the CRF (or in the electronic record) and in the database.

9 CONTENT OF REPORTS

All analysis results for the short-term double-blind period will be included in the short-term CSR while all the analyses specified for the combined short- and long-term treatment period will be included in the Final CSR.

10 CHANGES OF ANALYSIS FROM PROTOCOL

Changes from Protocol prior to short-term data base lock are summarized in the following table:

Changes	Reason for changes
Definition of Full Analysis Set was added.	To be consistent with other saxagliptin plus dapagliflozin studies.
Summary and analysis of SMBG data was updated.	To be consistent with other saxagliptin plus dapagliflozin studies.
Definition of Confirmed hypoglycemia was updated to consider all events with glucose values ≤ 70 mg/dL (3.9 mmol/L) as recorded in the hypoglycemia module of the CRF	To avoid error in summarizing data based on glucose values which were not collected using consistent methods.

Changes	Reason for changes
irrespective of the method using which glucose data were collected.	
MI sensitivity analyses for primary endpoint were added.	To be consistent with other saxagliptin plus dapagliflozin studies.

12 SUMMARY OF CUTOFFS FOR ANALYSES WHICH EXCLUDE RESULTS AFTER TREATMENT DISCONTINUATION

Assessment collected more than x days after last dose in the ST+LT treatment period are excluded from analyses		
Number of days		Assessment/measurement
1	Efficacy	fasting plasma glucose fasting C-peptide fasting insulin spot urinary glucose/creatinine ratio HOMA assessments Beta cell function for C-Peptide Beta cell function for insulin Insulin sensitivity for C-peptide Insulin sensitivity for insulin Insulin rstn for C-peptide Insulin rstn for insulin
4	Efficacy	SBP glucagon proinsulin urinary albumin to creatinine ratio biomarkers C-reactive protein N-terminal ProB-type Natriuretic Peptide lipids (Total-C, LDL-C, HDL-C, TG)
4	Safety	non-serious adverse events including non-serious hypoglycemic events vital signs hematology labs clinical chemistry labs
8	Efficacy	HbA1c body weight BMI waist circumference
30	Safety	SAEs (including hypoglycemic reported as SAEs) liver function tests ALT AST alkaline phosphatase total bilirubin

